5.4.2 Treatment Randomization

Once informed consent has been obtained and all eligibility criteria have been met, subjects will be randomized 1:1 to tivozanib or sorafenib using an IWRS. Subjects must begin treatment with study drug within 14 days after randomization. Specific instructions for use of the enrollment/randomization system will be provided in a separate manual.

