7.1.2 Cycle 1, Day 1 (Baseline) Visit

At the Cycle 1, Day 1 Visit, the following procedures and evaluations will be performed:

- Concomitant medications
- Adverse event assessments
- Study drug administration
- ECOG performance status
- Vital sign measurements
- Directed PE
- Hematology
- Serum chemistries
- Coagulation parameters
- Urinalysis
- Pharmacokinetics sample at hour 4 post dose
- Distribute study drug diary

Note: If ECOG performance status, PE, hematology, serum chemistry, coagulation parameters, and urinalysis were measured/performed within 7 days prior to this visit, they need not be repeated.

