7.4 Randomization and Blinding

The IWRS will be used for randomization and drug management (packaging of clinical supplies, shipping to study sites, and dispensing to subjects).

Subjects will be randomized in a 1:1 ratio (tivozanib: sorafenib) stratified by IMDC risk category (favorable; intermediate; poor) and prior therapy (two prior VEGFR TKIs; a prior checkpoint inhibitor [PD-1 or PD1 L inhibitor] plus a prior VEGFR TKI; a prior VEGFR TKI plus any other systemic agent). Once the strata have been identified, treatment will be randomly assigned to a subject within the strata using a complete permuted block design, in an unblinded fashion (open-label). In the event a subject had both 2 TKIs and a checkpoint inhibitor, the subject will be stratified according to the most recent line of therapy.

Subjects must begin treatment with study drug within 14 days after randomization.

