4.2 General Presentation Considerations

'Baseline' is defined as the last observation on or before Cycle 1 Day 1. Baseline assessments should occur within 7 days of Cycle 1 Day 1. 'End of Treatment' is defined as the last available observation up to 7 days after the last dose of study treatment. 'End of Study' is defined as the last available observation after 'End of Treatment'.

Durations are calculated as the stop date minus the start date plus one.

For elapsed time (e.g. time since the initial diagnosis) if the reference date is on or after the event date, then the elapsed time is the reference date minus the event date plus one. If the reference date is before the event date then the elapsed time is the reference date minus the event date.

Unscheduled assessments (laboratory data, ECG, or vital signs associated with nonprotocol clinical visits or obtained in the course of investigating or managing adverse events) will be included in listings, but not summaries. If more than one laboratory value is available for a given visit, the first valid observation will be used in summaries and all observations will be presented in listings. If it is not possible to determine which is the first measurement due to missing times then the average of all measurements for that time point will be used as the value for that time point.

Continuous data will be summarized in terms of the mean, standard deviation (SD), median, minimum, maximum, and number of observations, unless otherwise stated. Continuous data that are expected to be skewed will be presented in terms of the maximum, upper quartile, median, lower quartile, minimum, and number of observations. The minimum and maximum will be reported to the same number of decimal places as the raw data recorded in the database. The mean, median, lower quartile, and upper quartile will be reported to one more decimal place than the raw data recorded in the database. The SD will be reported to two more decimal places than the raw data recorded in the database. In general, the maximum number of decimal places reported shall be four for any summary statistic.

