4.5 Demographic and Other Baseline Characteristics

The following demographic and baseline characteristics will be summarized for subjects in the ITT population by treatment arm:

- Age at time of informed consent (in years, as a continuous variable)
- Age categorization (<65, >= 65 years)
- Gender (Male, Female)
- Race (White, Black/African American, Asian, American Indian/Alaska Native, Hawaiian Native/Other Pacific Islander, Unknown, Other, Decline to State)
- Ethnicity (Hispanic or Latino, Not Hispanic or Latino, Unknown, Decline to State)
- Geographic region [North America (NA), European Union (EU), Rest of World]
- Weight at screening (in kilograms)

- Height at screening (in centimeters)
- BMI at screening (in kg/m^2) calculated using weight and height at screening
- Baseline systolic blood pressure (<=140 mmHg, >140 mmHg)
- Baseline diastolic blood pressure (<=90 mmHg, >90 mmHg)
- IMDC risk category (Favorable, Intermediate, Poor)
- Prior therapy (Two Prior VEGFR TKIs, Prior Checkpoint Inhibitor Plus VEGFR TKI, Prior VEGFR TKI Plus Other Systemic Agent)
- Baseline Eastern Cooperative Oncology Group (ECOG) performance status (0, 1)
- Primary diagnosis:
 - Time from initial diagnosis to randomization (in months)
 - Time from most recent relapse or staging to randomization (in months)
 - Pathological diagnosis (Clear Cell, Clear Cell Component, Other)
 - Diagnosis confirmation method (Histology, Cytology, Other)
 - Stage at screening [Stage IV (metastatic), Local Recurrence]
 - Metastatic site location
 - Type of metastases (Multiple Metastases, Solitary Metastases, No Involvement, Unknown)
- Primary disease:
 - Number of metastatic sites per subject
 - Prior radiotherapy (Yes, No)
 - Prior chemotherapy setting (Neo-adjuvant, Adjuvant, Metastatic/Unresectable Therapy, Other, Unknown)
 - Prior nephrectomy (Complete Nephrectomy, Partial Nephrectomy, Other)

Since age is part of the inclusion criteria, age will be calculated as the number of complete years between a subject's birth date and the date of informed consent.

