4.7.1.2 Adjustments for Covariates

The potential influences of baseline characteristics and stratification factors on the primary PFS endpoint will be evaluated. These factors include the following:

- Age categorization (<65, >= 65 years)
- Race (White, Non-white)
- Gender (Male, Female)
- Baseline Eastern Cooperative Oncology Group (ECOG) performance status (0, 1)
- Time from initial diagnosis to randomization (< 1 year, >=1 year)
- Geographic region [North America (NA), European Union (EU), Rest of World]

- IMDC risk category (Favorable, Intermediate, Poor)
- Prior therapy (Two Prior VEGFR TKIs, Prior Checkpoint Inhibitor Plus VEGFR TKI, Prior VEGFR TKI Plus Other Systemic Agent)
- Number of metastatic sites involved (1, >=2)
- Baseline systolic blood pressure (<=140 mmHg, >140 mmHg)Baseline diastolic blood pressure (<=90 mmHg, >90 mmHg)

To assess the robustness of study conclusions to the choice of covariates, a sensitivity analysis will be performed.

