4.10 Changes in the Conduct of the Study or Planned Analysis

Protocol Version 4.0 was finalized on 01 October 2018. The administrative change was:

• A previously unspecified data cut-off date for the primary analysis was established to be 04 October 2018 with a targeted number of 242 PFS events.

The PFS event rate continues to decelerate. The study steering committee participated in a conference call on Thursday, August 30, 2018 and unanimously recommended performing the analysis rather than waiting for the additional events to reach the planned 255 PFS events. The reasons given were that the current patients have been on study for at least one year and may not progress for some time, and that the small reduction in events at the time of final analysis was unlikely to materially affect the results.

- The committee was concerned that based on the small number of patients remaining that can contribute to a PFS event, it could take another 5 months or more to get to 255 events.
- Some committee members expressed that based on the safety profiles they have observed during the study, they are keen to provide access to this drug to their patients.

This proposal was presented to the US FDA and they reported the decision is at the discretion of the Steering Committee and the sponsor.

Protocol Version 3.0 was finalized on 13 July 2016. Changes that have statistical implications are:

- the removal of the tertiary objective of exploring the correlation of serumneuropilin 1 (NPR-1) with clinical activity in subjects randomized to treatment with tivozanib or sorafenib.
- The addition of the tertiary objectives of exploring the relationship between tivozanib and sorafenib drug levels and activity as well as the relationship between the IP drug levels and AEs.

Subjects must begin planned treatment of the study drug within 14 days after randomization.

An exploratory analysis of PFS on the safety population was added to the SAP to account for subjects that were randomized to a treatment arm but not dosed due to external issues.

Best Overall Response criteria was updated to align with the RECIST 1.1 guidelines.

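### The SAP anchors baseline to first dose, not to open-label randomization, so blood pressure and some ECOG scores used in the ITT table, PFS covariate analysis and PFS subgroups can be measured after the arm is known

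*SAP*

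**What the plan says.** SAP 4.2 states that baseline "is defined as the last observation on or before Cycle 1 Day 1" and adds "Baseline assessments should occur within 7 days of Cycle 1 Day 1". It gives no separate definition for efficacy.

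Protocol 7.1 makes the day of first dose Day 1 and places that day's assessments before the dose. Protocol 5.4.2 sets the gap: "Subjects must begin treatment with study drug within 14 days after randomization". Protocol 7.4 says treatment is assigned "in an unblinded fashion (open-label"), so the arm is known from randomization.

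Protocol 7.1.2 lists vital signs and ECOG among the Cycle 1 Day 1 procedures. It waives the Day 1 repeat for only some of them, on this condition: "If ECOG performance status, PE, hematology, serum chemistry, coagulation parameters, and urinalysis were measured/performed within 7 days prior to this visit". Vital signs are not in that list, and the vital signs row of protocol Table 1 does not carry the corresponding footnote (i).

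SAP 4.5 ties weight, height and BMI to screening. It lists "Baseline systolic blood pressure (<=140 mmHg, >140 mmHg") and the diastolic equivalent simply as baseline items, so the 4.2 rule governs them. The same applies to ECOG, which SAP 4.7.1.2 lists as "Baseline Eastern Cooperative Oncology Group (ECOG) performance status (0, 1"). All three recur as PFS covariates (4.7.1.2) and PFS subgroups (4.7.1.6).

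SAP 4.4 defines ITT as everyone randomized. SAP 4.10 refers to "subjects that were randomized to a treatment arm but not dosed due to external issues".

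**The concern.** A factor used to adjust or subdivide a randomized comparison should be fixed before assignment. Otherwise the groups compared within each level need no longer be randomized groups. Here the rule allows measurement after site and subject know the arm.

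ECOG is a judgement made by unblinded staff. Blood pressure is a sensitive factor for these drugs: protocol 3.6.2 reports hypertension in 44.0% on tivozanib and 34.2% on sorafenib in the earlier Phase 3 trial, so staff could have a reason to act on it before the first dose.

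A never-dosed subject has no Cycle 1 Day 1. One programmer could carry the screening value and another could set baseline to missing, and the SAP does not choose between them.

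At stake is the credibility of the covariate sensitivity analysis, whose stated purpose is to test robustness, and of three PFS subgroup factors.

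**Working it through.** **1. Design effect.** The plan gives no figure for this point, so its main design figure is reproduced only to fix the hazard ratio (HR). SAP 4.9 assumes medians of 4 and 6 months, so HR = 4/6 = 0.667. Schoenfeld events = 4(1.960 + 1.282)²/(ln 0.667)² = 256, against 255 stated; power at 255 events is 0.899, against 90% stated. Nothing below changes these figures.

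**2. When baseline follows randomization.** Let G be the days from randomization to Cycle 1 Day 1 (0 to 14, protocol 5.4.2). Let S be the days from screening ECOG to Cycle 1 Day 1 (from G, or from 1 if G = 0, up to 21; protocol 7.1.1). An ECOG repeat is required only if S > 7.

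| G (days) | Baseline blood pressure | Baseline ECOG |
|---|---|---|
| 0 | order relative to randomization not specified | screening score can stand if S ≤ 7; otherwise repeated on Day 1, order not specified |
| 1 to 7 | after randomization | screening score can stand if G ≤ S ≤ 7; otherwise repeated after randomization |
| 8 to 14 | after randomization | S ≥ 8 always, so repeated after randomization |

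The waiver is permissive: a site may repeat ECOG anyway, and the later score then becomes baseline.

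The documents do not give G or S, so the share of ECOG baselines taken before randomization could be anything from 0% to 100%. As an illustration only, take S uniform over its allowed range and the waiver always used. The share is then 7/21 = 33% at G = 1, 1/15 = 7% at G = 7, and 0 from G = 8. It averages 12% with G uniform on 0 to 14.

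**3. Size under assumed behaviour.** Exponential PFS, true HR 0.667 at both levels of the factor, 30,000 subjects per arm. Prevalence, prognostic effect and reclassification rates are all assumptions.

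- *Blood pressure.* 30% have systolic pressure above 140, with prognostic HR 1.4; 30% of those on tivozanib are brought to 140 or below before dosing.
- *ECOG.* Half are ECOG 1, with prognostic HR 1.7; 10% or 20% of sorafenib ECOG 0 subjects are re-scored 1.

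| Scenario | Affected subgroup HR | Adjusted HR |
|---|---|---|
| Systolic ≤140 | 0.659 to 0.685 (+0.026) | 0.664 to 0.682 (+0.018) |
| ECOG 1, 10% re-scored | 0.666 to 0.706 (+0.040) | 0.659 to 0.682 (+0.023) |
| ECOG 1, 20% re-scored | 0.682 to 0.755 (+0.073) | 0.666 to 0.707 (+0.041) |

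The starting values differ from 0.667 only by sampling error. Repeat runs at 3,000 per arm reach +0.08 in the ECOG 1 subgroup and +0.045 adjusted.

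Hand check for blood pressure: 0.30 × 0.30 = 0.09 of the tivozanib arm joins the 0.70 already at ≤140, a fraction 0.09/0.79 = 0.114. Mean starting hazard rises by 1 + 0.114 × 0.4 = 1.046, and 0.667 × 1.046 = 0.697, or +0.03.

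Hand check for ECOG at 10%: 0.05/0.55 = 0.091 of the sorafenib ECOG 1 group has relative hazard 1/1.7 = 0.588. The mean is 1 − 0.091 × 0.412 = 0.963, and 0.667/0.963 = 0.693, or +0.026 at the start. The gap widens as the lower-risk subjects stay at risk longer.

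The >140 subgroup has no expected shift, because those who leave it are a random part of it (HR unchanged at 0.674). By the same reasoning the ECOG 0 subgroup has none in the ECOG scenarios.

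**4. Scale.** The 95% interval around 0.667 with 255 events is 0.667 × exp(±1.96 × 2/√255), or 0.52 to 0.85. With half the events it is 0.47 to 0.94.

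**The case against.** The strongest reply is that the reach is narrow and the bias hypothetical. Day 1 values are taken before the dose, so no drug effect enters them. Three of 11 listed factors are involved, in a sensitivity analysis and a graphical subgroup display with no planned interaction test. No passage describes antihypertensive treatment given between randomization and first dose, or re-scoring that differs by arm. The shifts in the working are small beside the intervals. All of this stands, and it limits the point to a cheap improvement.

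Several stronger readings are tempting, and the documents do not support them:

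- *Every ECOG and blood-pressure baseline is post-randomization.* A screening ECOG within 7 days can stand, and dosing on the day of randomization leaves the order open for both measures.
- *Never-dosed subjects have no baseline data, or drop out of the analyses.* Protocol 7.1.1 schedules ECOG and vital signs at screening, so values should exist. What is missing is a rule. Their number is not given, and SAP 3.2.1 censors subjects with no later tumor assessment at randomization, so most would add little information to a PFS comparison.
- *The >140 subgroup is biased too.* A single run at 3,000 per arm can suggest a shift of −0.03. Eight such runs averaged −0.002, with a between-run SD of 0.044 for that HR, so this is noise.
- *The Day 1 ECOG categories are bound to fail.* A score of 2 would have no level in the SAP. But protocol section 7 limits study drug to subjects who meet the criteria, so such a score would first be an eligibility question.

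**Conclusion.** The point holds in limited form. The only baseline rule is tied to first dose. In this open-label design it makes blood pressure a post-assignment measurement whenever dosing is at least a day after randomization, and it does the same for ECOG under the timings shown. It is also undefined for never-dosed ITT subjects.

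A reader might infer that the primary result is at risk. It is not: the stratified log-rank test and Cox model use IMDC risk and prior therapy as randomized (SAP 4.4, 4.7.1, 4.7.2).

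The size of any bias is unknown. Movements of about 0.03 to 0.08 in an affected subgroup HR and 0.02 to 0.045 in an adjusted HR require changes concentrated in one arm at the assumed rates. Their direction, here toward 1, follows from which arm is assumed to change. Changes that are equal between arms and unrelated to outcome give no shift. The concern is knowledge of assignment, not drug effect.

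**What to change.** Give two definitions in SAP 4.2.

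- For the ITT baseline table and the efficacy factors (4.5, 4.7.1.2, 4.7.1.6), baseline is the last observation before randomization. This includes screening values for never-dosed subjects. State how a measurement dated on the day of randomization is handled when its time is not recorded.
- For change from baseline in the safety analyses, keep the last pre-dose value up to and including Cycle 1 Day 1.

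The cost is SAP wording and one derived variable; screening ECOG and vital signs are already scheduled for everyone. The downside is that some efficacy baseline values will be older, up to the limit of the screening window, 21 days before first dose.

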absorption of tivozanib or sorafenib, major resection of the stomach or small bowel, or gastric bypass procedure.

19. Psychiatric disorder or altered mental status precluding informed consent or necessary testing.
20. Participation in another interventional protocol.

Drugs and treatments to be excluded

The following medications/treatments are prohibited during the study:

1. Chemotherapy, biological therapy (including cytokines, signal transduction inhibitors, monoclonal antibodies), immunotherapy or any other therapy for RCC.
2. Systemic hormonal therapy, with the exception of:
 - Hormonal therapy for appetite stimulation or contraception
 - Nasal, ophthalmic, inhaled and topical steroid preparations
 - Androgen suppression therapy for non-metastatic prostate carcinoma
 - Hormone replacement therapy for conditions such as adrenal insufficiency, hypothyroidism, etc.
 - Low-dose maintenance steroid therapy (equivalent of prednisone ≤ 10 mg/day) for other conditions
3. Treatment with radiotherapy.
4. Herbal preparations/supplements (including daily multivitamin/mineral supplement containing herbal components) or topical ointments containing herbal components.
5. Treatment with strong cytochrome P450 (CYP3A4) inducers or inhibitors (see Appendix C).
6. Treatment with full dose oral anticoagulants such as warfarin, acenocoumarol, fenprocoumon, or similar agents unless they have been on a stable dose for more than 2 weeks prior to enrollment. Full dose anticoagulation with low molecular weight heparin or unfractionated heparin administered subcutaneously is allowed.

Investigational product, dosage and mode of administration:

Tivozanib: 1.5 mg orally once daily.

Subjects will receive 1.5 mg tivozanib once daily beginning on Day 1 for 21 days followed by 7 days off treatment.

One cycle will be defined as 4 weeks in duration, consisting of 3 weeks on treatment and a week off treatment.

Cycles will be repeated every 4 weeks.

Name of sponsor/company: AVEO Pharmaceuticals, Inc.
Name of investigational product: Tivozanib Hydrochloride (AV-951) capsules
Reference therapy, dosage and mode of administration: 
Sorafenib: 400 mg orally twice daily
 
Subjects will receive 400 mg sorafenib twice daily continuously, beginning on Day 1. One cycle will be defined as 4 weeks of treatment. Cycles will be repeated every 4 weeks.

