- m. For subjects with stable disease or objective response at the time of treatment discontinuation, who discontinue for reasons other than radiological evidence of progressive disease, tumor assessments will continue to be collected (every 2 months during the first year [beginning from the date of the last scan performed prior to treatment discontinuation], every 3 months during the second year, and every 6 months thereafter) until disease progression is confirmed by independent radiology review or start of another therapy. A ±3 day visit window applies to tumor assessments for subjects that have discontinued study drug.
- n. Two blood samples for pharmacokinetic (PK) analysis will be collected at the following time points from all subjects: Cycle 1, Day 1- 4 hours post-dose and Cycle 1, Day 15- pre-dose (within 2 hours before dosing).
- o. After the 30-Day Follow-up visit, subjects will be contacted once every 3 months by the site to collect long-term survival data. Additional contacts may be made to support key analyses, such as the analysis of overall survival at the time of the final PFS analysis, and the final analysis of overall survival. A ±7 day window applies for the scheduled long term follow-up contacts.
- p. A ±2 day window applies to all visit procedures except study drug administration.
- q. The duration of treatment for tivozanib is 21 of 28 days, and for sorafenib is 28 of 28 days.
- r. All subjects will have an EOT visit when they permanently discontinue any further study treatment. The EOT visit will occur up to 7 days after the last dose of study drug. Assessments performed within 3 days of the EOT visit need not be repeated and may be documented as the EOT assessment (except for the response assessment which does not need to be repeated if performed within 30 days and showed progressive disease). Subjects starting new anti-cancer therapy after the last dose of study drug must complete the End of Treatment Visit assessments in advance of starting the new anti-cancer therapy.
- s. If additional visits are needed, these assessments may be obtained/ performed/ measured as clinically indicated.

TABLE OF CONTENTS

PROCEDURES IN CASE OF EMERGENCY	2
PROTOCOL SIGNATURE PAGE	3
1 SYNOPSIS.....	4
2 LIST OF ABBREVIATIONS AND EXPANDED TERM	20
3 INTRODUCTION	23
3.1 Background.....	23
3.2 Pharmacology	23
3.3 Safety Pharmacology	24
3.4 Toxicology	24
3.5 Pharmacokinetics	26
3.6 Previous Human Experience.....	26

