7.1 Procedures/Parameters to be Measured

See the Study Flowchart ([Table 1](#), beginning on page 12) for the timing of the procedures to be performed at each visit.

All subjects will be assessed by scheduled clinical, laboratory, and other diagnostic assessments throughout the study. Subjects will be treated on an outpatient basis, unless hospitalization is required for other reasons.

Subjects must voluntarily sign and date the study-specific Institutional Review Board (IRB)/Ethics Committee (EC)-approved informed consent before any study-related procedures (with the exception of disease assessment for screening if it was completed as part of standard of care) are performed.

All screening assessments are to be performed within **21 days** prior to first study drug dose, unless otherwise specified.

The day of first study drug administration will be considered **Day 1** of the study.

Clinic visits will take place according to the schedule of assessments. The visit window of ± 2 working days does not apply to study drug administration. Visit assessments will be performed prior to administration of the study drug for that day.

If significant changes from baseline are noted during the course of the study, additional unscheduled clinic visits may be undertaken by the investigator, or requested by the sponsor, in order to determine both the relevance of the finding(s) and the duration of the event(s).

All end-of-treatment assessments are to be performed within **7 days** following the last study drug dose unless delayed due to the occurrence of an adverse event. Note: subjects starting any new anti-cancer therapy must complete the End-of-Treatment Visit prior to starting the new anti-cancer therapy.

A follow-up visit will be performed **30 days (± 7 days)** following the last dose of study drug.

After the 30-Day Follow-up visit, subjects will be contacted once every 3 months by the site to collect long-term survival data.

Informed Consent

All subjects must take part in the informed consent process. Adequate time must be allowed for the subject to ask questions and make a voluntary decision. No protocol specific procedures, including screening procedures are to be performed until the subject has signed and dated an IRB/EC approved informed consent form (ICF). The signing of the ICF can occur outside of the 21-day screening period; however, all protocol related procedures must only be performed after signing of the consent.

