7.2 Study Drug Administration

7.2.1 Tivozanib Administration

Tivozanib will be administered orally, at a dose of 1.5 mg/day, beginning on Day 1 of Cycle 1. Subjects will receive tivozanib once daily for 3 weeks followed by 1 week off study drug (1 cycle = 3 weeks on, 1 week off). One cycle will be defined as 4 weeks of treatment. Cycles will be repeated every 4 weeks.

The prescribed daily dose of tivozanib is to be taken, preferably in the morning, with water. Tivozanib should be taken at least 1 hour before or 2 hours after ingesting any food or other medications. Grapefruit juice should not be ingested during the study. On days of a scheduled clinic visit, the dose of tivozanib should be taken at the clinic after visit procedures are completed. Treatment with tivozanib will continue if tolerated and in the absence of documented disease progression. If a dose is vomited or if a dose is missed for any reason, the dose should not be made up. If Day 1 of a cycle is delayed for any reason, the complete 21 days of tivozanib should be administered once the cycle is started. Only one tivozanib capsule should be taken each day.

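### The 7-day End of Treatment limit in SAP 4.2 can shut out the recorded EOT assessment, and tivozanib's rest week triggers this at a nominal cycle Day 1 stop

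*SAP*

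**What the plan says.** SAP 4.2 sets one rule for both arms: End of Treatment "is defined as the last available observation up to 7 days after the last dose of study treatment". It also keeps unscheduled assessments out of the summaries, and it defines End of Study as the last observation after End of Treatment.

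The protocol puts a similar limit on the visit itself. Table 1, note r: "The EOT visit will occur up to 7 days after the last dose of study drug". The same note ties the visit to permanent discontinuation. Protocol 7.1 adds an exception: the assessments fall within 7 days "following the last study drug dose unless delayed due to the occurrence of an adverse event". SAP 4.2 has no such exception.

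The arms differ in dosing. Table 1, note q: "The duration of treatment for tivozanib is 21 of 28 days, and for sorafenib is 28 of 28 days". Protocol 7.2.1: "Subjects will receive tivozanib once daily for 3 weeks followed by 1 week off study drug". On visit days the dose comes last: "On days of a scheduled clinic visit, the dose of tivozanib should be taken at the clinic after visit procedures are completed". Protocol 7.2.2 says the same for sorafenib.

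SAP 4.8.4 and 4.8.5 plan summaries by visit: change from baseline with rank-sum comparisons for laboratory values and vital signs, and shifts for laboratory grade, ECG, ECOG and physical examination. For laboratory by-visit summaries, 4.8.4 takes the first non-missing assessment recorded at each visit.

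**The concern.** A limit counted from the last dose treats a planned rest week as if it were time off study. For tivozanib, the seven rest days use up the whole allowance, so a stop at the next nominal Day 1 visit is already too late. The SAP wording does not then leave the End of Treatment value missing. It asks for the last available observation inside the limit, which is an earlier on-treatment visit or, for ECG, normally the baseline itself. The assessment actually made at stopping exists in the database but is not the one summarised as End of Treatment.

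At stake is whether the End of Treatment summaries of laboratory values, vital signs, ECG and ECOG describe subjects at stopping. Comparing safety and tolerability is a secondary objective, and a trigger built into only one arm's schedule makes the comparison at this time point hard to read.

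**Working it through.** This is a day count; no sample size or power figure is involved.

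**Inputs**
- Tivozanib cycle: 21 days on, 7 off (Protocol synopsis, 7.2.1). Cycle length 21 + 7 = 28 days, which reproduces the stated 4-week cycle.
- Sorafenib: 28 of 28 days (Table 1, note q).
- Visit window: "A ±2 day window applies to all visit procedures except study drug administration" (Table 1, note p). Protocol 7.1 words this as working days, which could widen it.
- End of Treatment limit: 7 days after last dose (SAP 4.2).
- Visit-day dose taken after procedures (7.2.1, 7.2.2), so a stop decided at a Day 1 visit precedes that day's dose.

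**Days since last dose at the next cycle's Day 1 visit**

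After a full tivozanib course the last dose is on cycle Day 21 and the next Day 1 is Day 29: 29 − 21 = 8.

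| Visit on day | Tivozanib, days since last dose | Within 7? | Sorafenib, uninterrupted |
|---|---|---|---|
| 27 | 6 | yes | 1 |
| 28 | 7 | yes | 1 |
| 29 (nominal) | 8 | no | 1 |
| 30 | 9 | no | 1 |
| 31 | 10 | no | 1 |

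Three of the five permitted days miss the limit for tivozanib; none does for uninterrupted sorafenib. A visit inside the rest week (Days 22-28, gaps of 1 to 7 days) always qualifies.

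**Which value the rule then selects (nominal days)**
- Stop at Cycle 3 Day 1: last dose day 49, stop visit day 57. The last scheduled visit inside the limit is Cycle 2 Day 1, day 29. 57 − 29 = 28 days before the stop visit; 49 − 29 = 20 days before the last dose. Later cycles repeat this for assessments made at every Day 1 visit.
- Stop at Cycle 2 Day 1: last dose day 21, stop visit day 29. The last scheduled visit inside the limit is Cycle 1 Day 15. 29 − 15 = 14 days before the stop visit; 21 − 15 = 6 days before the last dose.
- ECG: Table 1 schedules it only at screening, EOT and the 30-day visit, besides unscheduled visits, which are not summarised. The fallback is normally the screening ECG, which is also the SAP 4.2 baseline, so the End of Treatment shift is no change by construction.

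The recorded EOT value falls after the SAP's End of Treatment. It could count as End of Study, but a later 30-day visit value would displace it.

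**Routes that affect both arms**
- Adverse-event delay: Protocol 7.1 permits an EOT visit later than 7 days after last dose; SAP 4.2 does not count it.
- Interruption: Protocol 10.4.2 and 10.4.4 allow up to 4 weeks in either arm. If a subject off drug for more than 7 days then stops for good, a visit held at that decision is already outside the limit. After a full 4-week interruption it is at least 28 days after last dose, inside the 30-day visit window (30 ± 7 = days 23 to 37).

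**The case against.** The strongest case is that this is a one-day mismatch in a few descriptive safety cells.

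- **Progression stops often miss the scenario.** A reader might picture a subject stopping on day 57 because that day's scan shows progression. Protocol 7.2.4 and 11.1 keep such a subject on treatment until independent verification, so many progression stops will fall in mid-cycle, where the limit can work. This stands. The cases left are stops for toxicity or clinical deterioration, and progression verified late, that happen to fall at a Day 1 visit.
- **Direction.** A reader might infer that deterioration at stopping is understated mainly for tivozanib. The documents do not support that. The interruption route runs in both arms, and in the earlier trial of the same two drugs (Protocol 3.6.2) interruptions occurred in 38.5% of sorafenib and 20.8% of tivozanib patients, which could push the imbalance the other way. This stands.
- **Other summaries.** Adverse events are collected to 30 days after last dose, the 30-day visit repeats laboratory tests, vital signs, ECG and ECOG, and the SAP adds worst laboratory grade and maximum shift across visits. This stands and limits the consequence. Nor is there a between-arm test for ECOG, only shifts.
- **The by-visit rule.** SAP 4.8.4 uses what is recorded at each visit, so a programmer could fill the End of Treatment row from the EOT visit. No table shells are shown, and the row is inferred from the by-visit summaries. This stands only in part: 4.8.4 states that rule for laboratory data and does not say it overrides 4.2. Two stated conventions give different answers.

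**Conclusion.** The point holds. SAP 4.2, read literally, can replace a recorded EOT assessment with an earlier value. For tivozanib this happens at a nominal Day 1 stop after a full course (8 days against a limit of 7). In either arm it happens when an adverse event delays the visit beyond 7 days or when the stop follows an interruption of more than 7 days. The substituted value is nominally 28 days older than the stop visit from Cycle 3 Day 1 onward and 14 days older at Cycle 2 Day 1. For ECG it is normally the baseline.

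The rest-week figures assume that all 21 doses were taken on schedule, that the subject stops before the Day 1 dose, and that there was no visit in the rest week that the summaries can use.

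The reach is the by-visit End of Treatment summaries of laboratory values, vital signs, ECG and ECOG. PFS, OS, treatment-emergent adverse event and worst-grade laboratory summaries are not driven by this definition. A reader might multiply a guessed share of Day 1 stops by the 161 planned tivozanib subjects. The documents give no such share, and two of the five permitted visit days comply, so neither the number affected nor the net direction between arms can be computed. It is still worth correcting, because it is a stated rule with a wrong result.

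**What to change.** In SAP 4.2, define End of Treatment for summaries as the assessment recorded at the EOT visit, whatever the number of days since last dose, and state that this follows the by-visit rule in 4.8.4. Do not carry an earlier cycle visit or a baseline value into the End of Treatment row. List the days from last dose to the EOT visit by subject, and report the number of missing End of Treatment values by arm.

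The cost is one definition and one listed interval, on data already collected. The downside is that time since last dose will vary more between subjects and some End of Treatment values will be missing, possibly for reasons related to why the subject stopped. That is why the counts by arm should be shown.

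The protocol passages on EOT timing (Table 1 note r, 7.1 and 7.1.7) should be reconciled with each other, since only 7.1 allows an adverse-event delay, and with the tivozanib rest week. No particular visit rule is proposed here, and the SAP change does not depend on one.
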